8.1.3. Exploratory Endpoints and Analyses

The exploratory efficacy endpoints include change from baseline in 24-hours mean ambulatory SBP, DBP, heart rate, pulse pressure, body weight, HbA1c, and subjects requiring rescue medication. Analyses will be primarily based on ITT analysis set.

8.1.3.1. The placebo-adjusted change from baseline to week 12 in 24-hour mean ABPM SBP among subjects taking appropriate doses of three or more types of antihypertensive therapies at baseline

A summary and ANCOVA model will be presented as in section 8.1.1.1 using only subjects taking ≥ 3 types of antihypertensive therapies at baseline.

8.1.3.2. The placebo-adjusted 24-hour mean pulse pressure at week 12

The pulse pressure will be calculated as the difference between ambulatory SBP and ambulatory DBP. The 24-hour mean pulse pressure will be calculated as the mean of all hourly ambulatory pulse per day per clock hour. A summary and ANCOVA model will be presented as in section 8.1.1.1. The model will include baseline pulse pressure in place of baseline mean ambulatory SBP.

8.1.3.3. The placebo-adjusted change from baseline to week 12 in 24-hour ambulatory SBP among dippers and non-dippers

Dippers and non-dippers are defined as:

Dippers: nocturnal mean SBP \leq 90% of diurnal mean SBP;

Non-dippers: nocturnal mean SBP $>$ 90% of diurnal mean SBP.

The nocturnal time interval is between 12:00 AM - 8:00 AM and diurnal time interval is between 11:00 AM - 7:00 PM. The nocturnal time mean is computed as the mean of 8 (or fewer, if failures occur) hourly mean SBP values in the nocturnal range and the diurnal time mean SBP is computed as the mean of 8 (or fewer) hourly mean SBP in the diurnal range of times.

Summaries and ANCOVA models will be presented as in section 8.1.1.1 for dippers and non-dippers, respectively.

8.1.3.4. The placebo-adjusted change from baseline in 24-hour ambulatory HR at week 12

A summary and ANCOVA model will be presented as in section 8.1.1.1. In addition, baseline 24-hour ambulatory HR will also be included as covariate.

8.1.3.5. The placebo-adjusted change from baseline in body weight at week 12

A summary and ANCOVA model will be presented as in section 8.1.1.1. The model will include baseline weight in place of baseline mean ambulatory SBP. Baseline 24-hour ambulatory SBP will also be included as covariate.

8.1.3.6. The placebo-adjusted change from baseline in HbA1c at week 12

A summary and ANCOVA model will be presented as in section 8.1.1.1. The model will include baseline HbA1c in place of baseline mean ambulatory SBP. Baseline 24-hour ambulatory SBP will also be included as covariate.

8.1.3.7. The proportion of subjects requiring any rescue medication at week 12

The summary and analyses will be provided as in section 8.1.2.1 primary analysis.

8.2. STUDY 603B

For all efficacy analyses in study 603B the baseline will be defined as the last non-missing measurement prior to the first dose of double-blind study medication in 603B. Change is defined as the observed value minus baseline value. Similar to study 603A, the values from early termination visits, or values before the initiation of rescue medication in 603B will be used.

8.2.1. Primary Efficacy Endpoint and Analysis

The primary efficacy endpoint is the change from baseline (at week 12) to week 24 of the 24-hour mean ambulatory SBP in the bexagliflozin group compared to the change in the placebo group, testing for superiority at a two-sided 0.05 level of significance.

8.2.1.1. Primary Efficacy Analysis

Let $\mu_{\text{Bexagliflozin}, 24}$ and $\mu_{\text{PBO}, 24}$ represent the mean changes from baseline in 24-hour ambulatory SBP at Week 24 for bexagliflozin and placebo, respectively. The following hypotheses will be tested:

$$H_0: \mu_{\text{Bexagliflozin}, 24} = \mu_{\text{PBO}, 24} \text{ versus } H_1: \mu_{\text{Bexagliflozin}, 24} \neq \mu_{\text{PBO}, 24}$$

To test this hypothesis, an ANCOVA will be applied to analyze the mean change in 24-hour average ABPM SBP. The ANCOVA model will be used to adjust for the treatment group stratification by rescue medication/response as assessed by ABPM SBP at baseline (Week 12) (i.e., require rescue medication, not require rescue medication: SBP change ≤ 5 mmHg, >5 to ≤ 20 mmHg, >20 mmHg), baseline ABPM SBP value, and randomized treatment for study 603B as fixed effects.

Similar descriptive analysis as in Section 8.1.1.1 will be provided.

In addition, the interaction of the response stratification class (response ≤ 5 mm Hg, $5 <$ response ≤ 20 mm Hg, and response > 20 mm Hg, requiring rescue medication prior to week 24) and randomized treatment for study 603B will be added to the model. P-value for the type 3 test will be presented to check the significance of the interaction terms at 0.10 significant level. LS means, standard errors, and 95% CI for each combination of stratification class and treatment will be estimated from the model.

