3.5.2. Study 603B

Upon returning to the investigational site to return the ambulatory monitor at the conclusion of study 603A, subjects will begin participation in study 603B. They will receive a 12-week supply of bexagliflozin tablets, 20 mg.

At week 6 subjects will return to the investigational site for measurement of seated systolic and diastolic blood pressures. At week 12, subjects will visit the investigational site to consume the final tablet and to be fitted with an ambulatory monitor to record their baseline mean ambulatory blood pressure.

The following day, subjects will be randomized 1:1 to receive a 12-week supply of bexagliflozin tablets, 20 mg or bexagliflozin tablets, placebo.

An assessment of bexagliflozin population pharmacokinetics will also be conducted to include approximately 200 subjects. Samples will be taken between weeks 6 and 12. The population PK study design and analysis plan will be described in a designated study protocol and the analysis will be reported separately.

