3.7. DETERMINATION OF SAMPLE SIZE

The primary efficacy endpoint of study 603A is the change from baseline (Day 1) to week 12 in the 24-hour average SBP of the bexagliflozin group compared to the placebo group using superiority testing at an overall two-sided 0.05 level of significance.

The primary efficacy endpoint of study 603B is the change from week 12 to week 24 in the 24-hour average SBP in the bexagliflozin group compared to the placebo group using superiority testing at an overall two-sided 0.05 level of significance.

Although the patient population was anticipated to be nearly identical between the two studies, they were to be carried out as independent investigations with respect to their individual primary and secondary endpoints. The assumptions used to estimate the sample size for the primary endpoint of study 603A were:

1. The magnitude of the decrease from baseline (Day 1) to week 12 of the 24 h mean SBP in the bexagliflozin treatment arm will exceed that found in the placebo arm by 5 mm Hg;
2. The standard deviation of the change from baseline to week 12 will be 15 mm Hg for both the active and placebo groups;
3. The two-sided significance level is 0.05.

The assumptions to estimate the sample size required for the primary endpoint of study 603B were:

1. Bexagliflozin will remain effective for at least 24 weeks. The 24-hour average ABPM SBP will not change between Week 12 and Week 24.
2. Subjects who are randomized to receive placebo will show an increase in ABPM SBP of 4 mm Hg between Week 12 and Week 24.
3. The standard deviation of the change is 15 mm Hg for both the active and placebo groups.
4. The two-sided significance level is 0.05.

A sample size of 254 per arm is required for the measurement to have 85% power to attain significance for the second primary endpoint. It is estimated that 75% of subjects will have completed the 36 weeks of study treatment since the first randomization. Thus a total sample size of 680 subjects is planned for the first randomization. It is estimated that approximately 8% will drop out for the first 12 weeks. A sample size of 626 subjects at the end of the first 12 weeks will provide >95% power for the first primary endpoint.

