8.1.1.1. Primary Efficacy Analysis

Let $\mu_{\text{Bexagliflozin}, 12}$ and $\mu_{\text{PBO}, 12}$ represent the mean changes from baseline in 24-hour ambulatory SBP at Week 12 for bexagliflozin and placebo arm, respectively. The following hypotheses will be tested:

$$H_0: \mu_{\text{Bexagliflozin}, 12} = \mu_{\text{PBO}, 12} \text{ versus } H_1: \mu_{\text{Bexagliflozin}, 12} \neq \mu_{\text{PBO}, 12}$$

To test this hypothesis, an analysis of covariance (ANCOVA) will be applied to analyze the mean change in 24-hour average ABPM SBP. The ANCOVA model will include terms for diabetes status (history of type 2 diabetes mellitus [T2DM] or not), renal function (eGFR at screening as continuous variable), pre-treatment status (presently medicated for hypertension or not), randomized treatment, and the baseline 24-hour mean SBP as fixed effect covariates. Change from baseline will be the dependent variable. Analysis will be conducted on ITT analysis set. The last ABPM SBP post baseline will be used for the analysis.

Descriptive statistics (n, mean, Q1, median, Q3, SD, minimum, and maximum) will be reported by treatment group, along with the least squares means, differences between LS means, a 2-sided 95% confidence interval (CI) for each difference, p-value from the model effects.

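### The 603B primary ANCOVA uses the Day 1 ABPM only through a coarse stratum and the cumulative week-12 ABPM not at all, giving up some precision (0 to about 14% of residual variance)

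*SAP*

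**What the plan says.** SAP 8.2.1.1 defines the 603B primary ANCOVA with three terms: the four-class rescue/response stratum, "baseline ABPM SBP value, and randomized treatment for study 603B as fixed effects". Under the SAP's terminology (6.6), an unqualified week is a study week. The Week 12 baseline of 603B is therefore the cumulative week-24 reading, and it is in the model. Protocol 9.5 names only that reading as the adjustment.

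Two earlier ambulatory readings precede the second randomization at visit 9:

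- **Day 1.** A completed 24-hour ABPM is a condition of entry (SAP 3.5.1).
- **Cumulative week 12.** It is recorded at visits 5-6 (SAP 3.10, Table 1), and the second bottle is assigned only after it succeeds (SAP 3.8.1).

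The stratum classes the fall in mean SBP from Day 1 to cumulative week 24 as at most 5, over 5 to 20, or over 20 mm Hg, with a separate class for rescue (Protocol 5.4; SAP 3.8.1). The imputation model in SAP 8.2.1.2 uses the same two baseline terms plus treatment.

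On size, SAP 3.7 states: "A sample size of 254 per arm is required for the measurement to have 85% power". It assumes that the placebo arm "will show an increase in ABPM SBP of 4 mm Hg between Week 12 and Week 24", that on bexagliflozin "The 24-hour average ABPM SBP will not change between Week 12 and Week 24", and that "The standard deviation of the change is 15 mm Hg for both the active and placebo groups".

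**The concern.** One 24-hour reading mixes a subject's usual SBP with variation particular to that session. Earlier readings on the same subject help to separate the two, so they can predict the week-36 value beyond what the week-24 reading predicts. Both were taken before the second randomization, so adjusting for them cannot bias the 603B comparison and leaves the estimated treatment difference the same quantity.

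The stratum holds the Day 1 information in three broad bands, and nothing in the model holds the cumulative week-12 information. At stake is the width of the confidence interval in the study that fixes the trial size. The test's validity is not in question.

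**Working it through.** **Inputs from SAP 3.7 and 3.5.2.** The difference is 4 mm Hg (placebo +4, bexagliflozin 0) and the SD of change is 15. "The two-sided significance level is 0.05", power is 85%, and allocation is 1:1.

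**The plan's own figure.**
- n per arm = 2(1.960 + 1.036)² × 15² / 4² = 253. The SAP states 254.
- Power at 254: 4 / (15 × √(2/254)) = 3.005, and Φ(3.005 − 1.960) = 85.2%.
- Total: 508 / 0.75 = 678. The SAP states 680.

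The figure reproduces. It is for an unadjusted change score and takes no credit for covariates.

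**Assumptions not in the documents.** No correlation between ABPM sessions is given, so several structures were tried. Four readings (Day 1 and cumulative weeks 12, 24 and 36) were simulated. They were scaled so that the week 24-36 change has SD 15, with an assumed mean of 148 mm Hg, an assumed drug effect of 5 mm Hg, and the Day 1 entry cut at 135 mm Hg. The rescue class was not simulated.

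**Closed form under equal correlation ρ.** With k prior readings, residual variance = σ²[1 − kρ² / (1 + (k−1)ρ)].
- ρ = 0.4: one reading 0.840σ², three readings 0.733σ², a cut of 12.7%.
- ρ = 0.8: one reading 0.360σ², three readings 0.262σ², a cut of about 27%.

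These cuts are relative to adjusting for week 24 alone. The entry cut lowers them to 10.1% and 23.3%, and the planned stratum already recovers 3.6% and 11.0%. What remains relative to the planned model:
- ρ = 0.4: 1 − (1 − 0.101)/(1 − 0.036) = 6.7%
- ρ = 0.8: 1 − (1 − 0.233)/(1 − 0.110) = 13.8%

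**Planned ANCOVA against the same model plus Day 1, cumulative week 12 and 603A arm:**

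| Assumed structure | Residual SD, planned → extended | Variance cut | Power at 254 per arm |
|---|---|---|---|
| Equal, 0.4 | 12.14 → 11.72 | 6.7% | 96.0% → 97.0% |
| Equal, 0.6 | 12.65 → 11.97 | 10.5% | 94.6% → 96.5% |
| Equal, 0.8 | 13.05 → 12.12 | 13.8% | 93.2% → 96.1% |
| Half equal, half AR(1), 0.5-0.7 | 12.87-13.64 → 12.75-13.47 | 1.9-2.5% | gain under 1 point |
| AR(1), 0.5-0.8 | 12.99-14.22, unchanged | 0% | 93.4-88.7%, unchanged |

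A further structure has true SBP drifting over time plus independent session noise. With reliability 0.6-0.9, the cut is about 3-8% when the 12-week autocorrelation is 0.9-0.95, and about 1-8% when it is 0.8-0.95. Pure AR(1) gives zero because the week-24 reading then carries everything that the earlier readings know. That requires a reading with no session noise.

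**Where the gain comes from (equal correlation 0.4-0.8).** Cumulative week 12 alone gives 5.6-11.6%, and Day 1 alone gives 1.9-4.8%. The 603A arm belongs with the week-12 value because that reading was taken on drug or placebo. Leaving the arm out costs only 0.1-0.3 percentage points.

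**In subjects.** Under equal correlation, n per arm for 85% power falls from 166 to 155 (ρ = 0.4) or from 192 to 165 (ρ = 0.8). That is 22 to 54 subjects in total.

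**The case against.** The strongest case against is that nothing is broken. The planned model adjusts for the 603B baseline and for the factor balanced at the second randomization. It has no bias or error-rate problem, and it exceeds its stated power under every structure tried. All of that stands.

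Several stronger readings are tempting and are not supported:

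- **That power would rise from 85% to about 88-90%.** A reader might apply the 7-14% cut to the SD of 15. But that SD belongs to an unadjusted change score, while the cut is relative to the planned ANCOVA. With equal correlation, one-baseline ANCOVA already leaves only (1 + ρ)/2 of the change-score variance (0.70 at 0.4, 0.90 at 0.8), and the stratum lowers it further.
- **That 603B has almost no slack.** A reader might set 680 × 0.75 = 510 against 508. The 508 is the need of an unadjusted test. Under equal correlation the planned ANCOVA needs about 332-384. Also, 510 counts 36-week completers, while the primary analysis also takes early-termination and pre-rescue values from randomized subjects (SAP 8.2).
- **That Day 1 is left out.** It is coarsened into the stratum, not omitted.
- **That 7-14% is a property of the trial.** It follows from an assumed equal correlation. With the SD of change fixed at 15, ρ = 0.8 also implies a single-session SD of 15/√0.4 = 23.7 mm Hg. Sessions are 12 weeks apart, so some decay is plausible.

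The added covariate also has practical drawbacks. Cumulative week-12 values can be missing after two failed recordings (SAP 3.10), and subjects with persistent hypertension may complete visits 5-6 early (SAP 3.8.1), so its timing varies.

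**Conclusion.** The point holds as an optional gain in precision. The 603B primary model uses Day 1 coarsely and cumulative week 12 not at all, although both readings precede the second randomization. The supportable range for the cut in residual variance is 0 to about 14%: about 7-14% under equal correlation of 0.4-0.8, about 3-8% with slowly decaying correlation plus session noise, and 0% under pure AR(1). Most of any gain comes from the cumulative week-12 value.

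Under equal correlation, power at 254 per arm rises by about 1-3 points, from about 93-96% to about 96-97%. These figures rest on the SAP's difference of 4 and SD of change of 15, and on correlation structures that the documents do not give. The benefit is modest, but it would offer some protection if the true effect or retention fell short of plan.

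**What to change.** Before unblinding, amend SAP 8.2.1.1 to add the continuous Day 1 24-hour mean SBP, the cumulative week-12 24-hour mean SBP and the 603A arm as covariates. Add the same terms to the imputation model in 8.2.1.2. Write cumulative week 12 in full, so that it is not confused with the 603B baseline. State that a missing cumulative week-12 value will be imputed from pre-randomization covariates only. Because SAP 8.2.2 refers back to 8.2.1.1, say whether the secondary models take the matching earlier values of their own endpoint.

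No new data or visits are needed. The cost is a few degrees of freedom, one missing-covariate rule, and acceptance that the week-12 reading is early for subjects who complete visits 5-6 ahead of schedule.

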8.2.1.2. Sensitivity Analysis

- If subject has received rescue medication and has an ABPM value after rescue medication, this value will be analyzed as an outcome. Per protocol, if subject requires rescue medication, ABPM will be taken before starting rescue medication. In such case, ABPM is not normally measured again after rescue medication. This sensitivity analysis will only be conducted if >5 subjects have post rescue medication values.
- Subjects without scheduled Week 24 assessments will be excluded from the analysis.
- A tipping point analysis will be conducted if there are subjects missing Week 24 assessment. Steps below will be followed:
 - If subject used rescue medication or discontinued during withdrawal period, value will be considered as missing.
 - A regression model will be used to impute the missing change value using SAS PROC MI procedure. Covariate will include baseline 24-hr mean SBP, the treatment group stratification by response as assessed by ABPM SBP at baseline (Week 12), and randomized treatment for study 603B. One hundred datasets will be imputed.
 - If subjects with missing value are in the placebo treatment arm, the imputed values will be used.
 - If the subject is in the bexagliflozin treatment arm, a series of δ will be added to the imputed values. The δ value will range from 0.5 to 5, with step size equals 0.5.
 - Same ANCOVA analysis from Section 8.2.1.1 will be conducted for each imputed dataset and δ . Results will be combined using PROC MIANALYZE in SAS.
- Wilcoxon rank sum test will be conducted including all Week 24 ABPM SBP values. If subject requires rescue medication, ABPM before starting rescue medication will be used; for a subject who has no post baseline assessment, the worst outcome within the treatment group (i.e., change from baseline = the maximum increase from baseline in the same treatment group) will be considered.

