### Study 603B, cumulative weeks 25-36

[figure not shown]
- Obtain 24-h ABPM and collect safety data
- Prescribe rescue medication if SBP shows an increase of 30 mm Hg from baseline or exceeds 189 mm Hg in office measurements and continue study activities

Additional study procedures for safety and efficacy endpoint assessment will be performed as outlined in the study schedule.

The effectiveness and safety analyses will be conducted after all subjects have completed or withdrawn from study 603B.

To allow safety data to be collected for up to 36 weeks of exposure the study will not be stopped for overwhelming efficacy. The DMC will review the unblinded safety data at approximately 2 month intervals and may recommend protocol modification or early stopping due to safety concerns.

The integrated program is illustrated in Figure 1.

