### 9.2 Determination of Sample Size

The primary endpoint of study 603A is the change from baseline (Day 1) to week 12 in the 24-hour average SBP of the bexagliflozin group compared to the placebo group using a superiority testing at an overall two-sided 0.05 level of significance.

The primary endpoint of study 603B is the change from week 12 (cumulative week 24) to week 24 (cumulative week 36) in the 24-hour average SBP in the bexagliflozin group compared to the placebo group using a superiority testing at an overall two-sided 0.05 level of significance.

The assumptions to estimate the sample size for the primary endpoint of study 603A are:

1. The magnitude of the decrease from baseline (Day 1) to week 12 of the 24 h mean SBP in the bexagliflozin treatment arm will exceed that found in the placebo arm by 5 mm Hg;
2. The standard deviation of the change from baseline to week 12 will be 15 mm Hg for both the active and placebo groups;
3. The two-sided significance level is 0.05.

The assumptions to estimate the sample size required for the primary endpoint of study 603B are:

1. Bexagliflozin will remain effective for at least 24 weeks. The 24-hour average ABPM SBP will not change between week 12 and week 24 (cumulative week 24 and week 36).
2. Subjects who are randomized to receive placebo will show an increase in the ABPM SBP of 4 mm Hg between week 12 and week 24 (cumulative week 24 and week 36).
3. The standard deviation of the change is 15 mm Hg for both the active and placebo groups.
4. The two-sided significance level is 0.05.

A sample size of 254 per arm is required for the measurement to have 85% power to attain significance for the second primary endpoint. It is estimated that 75% of subjects will have completed the 36 weeks of study treatment since the first randomization. Thus a total sample size of 680 subjects is planned for the first randomization. It is estimated that approximately 8% will drop out for the first 12 weeks. With a sample size of 626 subjects at the end of study 603A, it will provide >95% power for the first primary endpoint.

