## 9.5 Primary Efficacy Endpoints

The primary endpoint of study 603A is the change from baseline (Day 1) to week 12 of the 24 h mean SBP in the bexagliflozin group compared to the change in the placebo group, testing for superiority at a two-sided 0.05 level of significance.

The primary endpoint of study 603B is the change from week 12 to week 24 (cumulative week 24 to week 36) of the 24 h mean SBP in the bexagliflozin group compared to the change in the placebo group, testing for superiority at a two-sided 0.05 level of significance.

For the primary efficacy assessment in study 603A, an analysis of covariance (ANCOVA) will be applied to analyze the mean change from baseline to week 12 of the 24-hour average ABPM SBP, adjusted for diabetes status, renal function, medicated or unmedicated status, and baseline ABPM SBP value. Least squares means with 95% confidence intervals (CIs) will be generated for the difference between the treatment groups at week 12. If a subject receives rescue medication or is withdrawn from the study early, the last post baseline observed value will be used for the primary analysis time point of week 12.

For the primary efficacy assessment in study 603B, a similar ANCOVA method will be applied, adjusted by the ABPM SBP evaluations at week 12 (cumulative week 24). Changes from week 12 to week 24 ABPM SBP will be analyzed. Least squares means with 95% CIs will be generated for the difference between the treatment groups at week 24.

Additional sensitivity analyses will be conducted as follows for missing data due to early withdrawal of the study or receiving rescue medications.

- Cumulative week 12 and week 36 evaluations after rescue medication will be used in the analyses in place of evaluations prior to the rescue medication
- Analyses will be based on subjects without rescue medication
- Tipping Point analysis will be conducted as follows:
  - Subjects in the bexagliflozin treatment arm who discontinue study participation or initiate rescue medication, will be analyzed assuming that their treatment effect has worsened by  $\delta$  (where  $\delta = 0.5$  to 5, with steps of 0.5) compared to the reduction of SBP for subjects who are in the study without rescue medication.

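### SAP 8.2.1.2 (603B) wrongly treats post-rescue ABPM as unusual, makes one protocol sensitivity analysis conditional and replaces another, and section 12 lists neither change

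*SAP*

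**What the plan says.** **Protocol, conduct.** For cumulative weeks 25-36 (section 3.1.3 and Table 1 in 5.7), an ABPM is obtained and rescue is prescribed if office SBP has risen 30 mm Hg from baseline or "exceeds 189 mm Hg in office measurements and continue study activities". Sections 7.10-7.11 and Appendix 1 schedule an ABPM at visits 10-11 (cumulative week 36), with no exemption for rescued subjects.

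**Protocol, analysis.** Section 9.5 lists sensitivity analyses for rescue and early withdrawal. The first: "Cumulative week 12 and week 36 evaluations after rescue medication will be used in the analyses", in place of the pre-rescue values. The second: "Analyses will be based on subjects without rescue medication". The third is a tipping-point analysis. None depends on a minimum count.

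**SAP.** In 8.2.1.2 the first bullet would analyse a post-rescue ABPM as an outcome. It notes that an ABPM is taken before rescue and continues: "In such case, ABPM is not normally measured again after rescue medication". It then limits the analysis to the case where more than 5 subjects have such values. The second bullet reads: "Subjects without scheduled Week 24 assessments will be excluded from the analysis". Under SAP 6.6, week 24 here means 603B study week 24, which is cumulative week 36. Among sensitivity analyses, section 12 records only the added Wilcoxon test.

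**The concern.** The 603B primary analysis uses the last ABPM before rescue (Protocol synopsis; SAP 8.2). That value is taken because pressure has risen. The design assumes a rise on placebo and none on bexagliflozin, so more rescues are expected on placebo. Holding those subjects at their pre-rescue value would then tend to widen the difference compared with using what was observed at week 36. Pre-rescue handling can be defended, but a reader will want to know how far the result depends on it.

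The protocol's first two sensitivity analyses answer that directly, one with observed post-rescue values and one without the rescued subjects. In the SAP the first may not run, and the second is replaced by a rule based on attendance. If the threshold is not met, no 603B sensitivity analysis uses an observed post-rescue value. Whether or not it is met, none is restricted to subjects unrescued during withdrawal.

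**Working it through.** **1. Is a post-rescue ABPM scheduled in 603B?**

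- *Rescue after visit 9 and before visit 10.* The subject continues and reaches the ABPM at visits 10-11. Where the protocol wants the rescue-time ABPM to stand in for a scheduled one, it says so: weeks 1-6 use visits 10-11 as termination visits, and weeks 7-12 use visits 5-6. Weeks 25-36 carry no such instruction. Section 9.5 also presupposes that week-36 values after rescue exist.
- *Criterion first met at visit 10.* Appendix 1 has no visit between visit 9 (week 24 + 1 day) and visit 10 (week 36). The ABPM begun at visit 10 is then the pre-rescue value, and none follows.

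The SAP sentence therefore fits the second case and not the first. A similar premise fits 603A better: SAP 8.1.1.2 explains that a rescued subject there terminates or moves into 603B.

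**2. Does the second SAP bullet exclude rescued subjects?** Its trigger is a missing scheduled assessment. The matching 603A bullet (SAP 8.1.1.2) describes it as concerning subjects who did not complete 12 weeks of treatment. A subject rescued in week 30 who attends visits 10-11 has the assessment and stays in.

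**3. What else in the SAP covers rescue?** The Wilcoxon test keeps the pre-rescue ABPM. The subgroups in 8.2.3.2 use rescue status before the second randomization. The tipping-point analysis sets values after rescue or discontinuation in the withdrawal period to missing, imputes them, and adds 0.5 to 5 mm Hg on bexagliflozin only.

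**4. Design figures (Protocol 9.2).** Inputs: "The two-sided significance level is 0.05"; "Subjects who are randomized to receive placebo will show an increase in the ABPM SBP of 4 mm Hg", with no change on bexagliflozin; "The standard deviation of the change is 15 mm Hg for both the active and placebo groups"; power 85%.

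n per arm = 2 × (1.960 + 1.036)² × 15² / 4² = 252.5, so 253 by the normal approximation. A noncentral t calculation gives 84.9% power at 253 and 85.1% at 254. The stated 254 is reproduced, so the total is 2 × 254 = 508.

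**5. Chance that the more-than-5 condition is met.** It needs at least 6 of 508, or 1.2%. The documents give no rescue rate. Assume a binomial count in which r is the proportion with a post-rescue week-36 ABPM:

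| r | expected count | P(at least 6) |
|---|---|---|
| 0.5% | 2.5 | 4% |
| 1% | 5.1 | 40% |
| 2% | 10.2 | 94% |
| 3% | 15.2 | >99% |

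Because r counts only rescue begun before visit 10, it is lower than the overall rescue rate.

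A rough guide to that overall rate borrows the ABPM SD of 15 for one office reading, which is an assumption. A rise of 30 mm Hg or more then has probability 1 − Φ(30/15) = 0.0228 at mean 0 and 1 − Φ(26/15) = 0.0415 at mean +4. That is about 6 and 11 of 255 per arm (680 × 0.75 / 2 = 255). This ignores the criterion of exceeding 189 mm Hg. Three-day confirmation and the lack of interim visits would lower the usable count, so it may fall on either side of the threshold.

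**6. Size if the condition is not met.** Shift in the difference = (excess placebo rescues / 254) × (pre-rescue minus post-rescue ABPM, assumed):

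- 1 subject, gap 15: 1/254 × 15 = 0.06 mm Hg
- 5 subjects, gap 10: 0.20 mm Hg
- 5 subjects, gap 20: 0.39 mm Hg
- 5 subjects, gap 25: 0.49 mm Hg, about 12% of 4
- 5 subjects, gap 30: 0.59 mm Hg

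The threshold counts both arms together, so 5 on placebo and none on bexagliflozin is the extreme split.

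**The case against.** The other side has four good arguments.

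- **The SAP sentence is hedged and partly right.** It says *not normally*, and the same bullet still provides for analysing any post-rescue value. With no visit between 9 and 10, rescue found on schedule is found at visit 10, where the sentence is accurate. A reader might infer that every rescued 603B subject has a later ABPM, or that the SAP denies any post-rescue value. The documents support neither. What stands is that rescue begun earlier, through unscheduled contact or the home readings allowed in Protocol 5.7, is followed by a scheduled ABPM.
- **The tipping-point analysis discards the pre-rescue value.** It does, and at small delta it may come close to a no-rescue result, so it would be wrong to say that nothing tests carry-forward. But it rests on imputation, uses no observed post-rescue value, and is not restricted to unrescued subjects.
- **The second bullet can be read another way.** Since SAP 8.2 uses values before rescue, a subject rescued mid-period could be said to have no usable scheduled value. That reading is possible, but the bullet does not state it, and the wording needs settling either way.
- **A minimum count is ordinary SAP detail.** Protocol 9.1 calls its text a summary, and the threshold can fail only when few values exist. That limits the harm. It does not explain why section 12, which records departures from the protocol, omits both changes.

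**Conclusion.** The point holds in limited form. For subjects rescued between the second randomization and visit 10, the SAP sentence conflicts with the protocol schedule. One protocol analysis has become conditional, another is replaced by a rule that does not mention rescue, and neither change is recorded.

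The effect is probably small. If the condition is not met, the unexamined shift is about 0.5 mm Hg at the extreme split with an assumed gap of 25 mm Hg (0.59 at 30), and well below that in milder cases. If about 2% or more of subjects have post-rescue values, the first analysis would most likely run anyway. These figures rest on assumed rescue rates and gaps, because the documents give none.

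Two stronger conclusions are tempting. One is that the mistaken premise caused the loss of the no-rescue analysis. The loss is plain in the text, but its cause is inference. The other is that the 603B primary result is compromised. Its estimate, test and sample size are unaffected; only the supporting evidence is thinner than the protocol planned. The change should be made, but it is not critical.

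**What to change.** In SAP 8.2.1.2:

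1. Correct the sentence. Subjects who start rescue after the second randomization and before visit 10 are scheduled for the week-36 ABPM; those who first meet the criterion at visit 10 have no later one.
2. Run the analysis with the observed week-36 ABPM regardless of rescue, for all subjects who have one, without the more-than-5 condition. If the condition is kept, record and justify it in section 12.
3. Restore the protocol's no-rescue analysis as its own bullet, excluding subjects who start rescue between cumulative weeks 24 and 36. Keep it separate from exclusion for a missing week-24 assessment.
4. List any remaining departure from Protocol 9.5 in section 12.

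The cost is SAP wording and two extra model runs on data already scheduled. Sample size, visits and rescue rules do not change.
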